**g. Study Endpoint(s)**

The study will terminate after 10 patients have been enrolled and have undergone surgery with use of the study device and 10 patients have undergone the standard of care and completed the survey. The primary outcome measure is device feasibility as measured by a surgeon questionnaire, which is completed at the end of every surgery. Secondary outcome measures include the time needed to obtain laparoscopic access using the device, as well as monitoring for adverse events. Another secondary outcome measure includes patient questionnaire to assess satisfaction.

If there is clear evidence of a lack of device feasibility through surgeon questionnaire review, or if there are any adverse events recorded that are related to the device and which endanger the health of a patient, the project leader will evaluate this information and decide whether any modifications or termination of the protocol are indicated.

---

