Pilot Study to Establish Safety and Ease of Use of a TauTona Pneumoperitoneum Assist Device (TPAD) for Laparoscopic Surgery

NCT04392635

August 19, 2024

Statistical Analysis Plan

Statistical Methods

For surgeon and patient questionnaire answers, a Wilcoxon test will be performed for each answer against a theoretical median of 4.0 (best). Since the insertion of the Veress needle should not significantly impact the final outcome of the entire laparoscopic procedure, analysis assumes that the theoretical median for each answer should be 4.0. Further, the standard of care is assumed to provide the current best care, so its theoretical median should be 4.0.

Determination of Sample Size

There were no statistically powered sample size requirements for this study. Based on the end points, the sample size of 15 for each group would be sufficient to determine bruising and the ability of the TPAD device to function as intended as compared to the control group.

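### The SAP calls 15 per group sufficient to judge the device's function against control, but its only stated test does not compare the arms and is insensitive at that size under the conventional exact version

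*SAP*

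**What the plan says.** The SAP's Determination of Sample Size section opens with "There were no statistically powered sample size requirements for this study". Its next sentence says "the sample size of 15 for each group would be sufficient to determine bruising" and, in the same breath, "the ability of the TPAD device to function as intended as compared to the control group". This point concerns only the second half, on function.

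The SAP's Statistical Methods section specifies one analysis, for surgeon and patient questionnaires: "a Wilcoxon test will be performed for each answer against a theoretical median of 4.0 (best"). For the control arm it adds that "the standard of care is assumed to provide the current best care, so its theoretical median should be 4.0". No between-arm test appears. Significance level, sidedness, p-value method, effect size, margin and a rule for concluding that the device works are all absent.

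Protocol section 2.g makes the questionnaire the main endpoint: "The primary outcome measure is device feasibility as measured by a surgeon questionnaire, which is completed at the end of every surgery". The same section ends the study once "10 patients have been enrolled and have undergone surgery with use of the study device", plus 10 standard-of-care patients. Section 1.a also gives 10 and 10. Section 8.a plans an enrolment of 30, which fits the SAP's 15 per group.

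**The concern.** The SAP's first sentence makes no promise about what the sample can show. The second makes one, and it is comparative. A reader would take it that the trial, at this size, can tell whether the device performs acceptably next to standard practice.

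The stated test cannot carry that conclusion. Its reference is a fixed number, so control answers play no part in testing the device answers. Its null hypothesis is also the best possible result, so non-rejection is the outcome that favours the device. With few patients, non-rejection is easy to obtain. Set beside a sentence that already calls the sample sufficient, a weak non-significant result could be taken as adequate evidence of function.

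**Working it through.** **The plan's own figure.** The 15 per group cannot be reproduced, because the SAP gives no significance level, power, effect or margin.

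**Inputs from the documents.** n = 15 per group (SAP); n = 10 per group (Protocol 1.a and 2.g); Wilcoxon test of each answer against 4.0, described as best (SAP).

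**Assumptions.** 4.0 is the top of the scale. Ratings are independent. The level is 5%. The share of uses rated below best, p, is not in the documents, so a range is shown.

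**Step 1: what the test needs in order to reject.** Ratings of 4 give zero differences and drop out. All other differences are negative. With k ratings below 4, the exact two-sided p-value is 2 × (1/2)^k.
- k = 5: 2/32 = 0.0625, not significant.
- k = 6: 2/64 = 0.031, significant.

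So the exact two-sided test needs k ≥ 6 at any n.

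**Step 2: power of the exact two-sided test.** Power = P(Bin(n, p) ≥ 6). For n = 15 and p = 0.30 this is 1 − (0.0047 + 0.0305 + 0.0916 + 0.1700 + 0.2186 + 0.2061) = 0.278.

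| Below best | n = 15 | n = 10 |
|---|---|---|
| 20% | 6.1% | 0.6% |
| 30% | 27.8% | 4.7% |
| 40% | 59.7% | 16.6% |
| 50% | 84.9% | 37.7% |

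**Step 3: dependence on the test version.** If all low scores are tied, the normal approximation without continuity correction gives z = √k. At k = 4, z = 2.0 and p = 0.046, so it rejects at k ≥ 4. With the correction, k = 4 gives z = (5 − 0.5)/2.5 = 1.8 (not significant) and k = 5 gives z = (7.5 − 0.5)/3.354 = 2.09 (significant). At n = 15 and 30% below best:

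| Version | Rejects at | Power |
|---|---|---|
| Exact, two-sided | k ≥ 6 | 27.8% |
| Exact, one-sided | k ≥ 5 | 48.5% |
| Normal, corrected, two-sided, tied | k ≥ 5 | 48.5% |
| Normal, uncorrected, two-sided, tied | k ≥ 4 | 70.3% |
| Normal, corrected, one-sided, tied | k ≥ 4 | 70.3% |
| Normal, uncorrected, one-sided, tied | k ≥ 3 | 87.3% |

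If the low scores spread over two or three levels below best, simulated two-sided normal power is about 30–38% with the correction and 49–53% without.

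**Step 4: would adding a comparison rescue the claim?** Neither document plans one, so this is illustrative. The power of Fisher's exact test is the sum, over all pairs of below-best counts with two-sided p < 0.05, of the product of the two binomial probabilities. For 10% v 30% below best it is 14.9% at 15 per group and 5.7% at 10. For 10% v 50% it is 53.6% and 29.5%. Fisher's test is conservative. A Mann–Whitney test with normal approximation gives about 26% for 10% v 30% at 15 per group.

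**Step 5: precision.** The Wald half-width is 1.96 × √[(p1(1 − p1) + p2(1 − p2))/n]. At n = 15:
- 10% v 10%: 1.96 × √(0.18/15) = 0.215
- 10% v 30%: 1.96 × √(0.30/15) = 0.277
- 50% v 50%: 1.96 × √(0.50/15) = 0.358

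At n = 10 the first and last become 1.96 × √(0.18/10) = 0.263 and 1.96 × √(0.50/10) = 0.438.

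**The case against.** A reader might infer that the SAP's own test would usually miss a device rated below best in 30% of uses. The documents do not support that as a flat statement. The miss rate is 72% for the exact two-sided test, about 52% for the exact one-sided test or the corrected two-sided normal test with tied scores, and 30% for the uncorrected two-sided normal test with tied scores. The SAP does not say which applies.

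The 30% is also a reviewer's figure. With 30% below best the median is still 4.0, so non-rejection is not an error about the hypothesis that the SAP states. The median leaves 4.0 only when more than half the ratings do, and there the exact two-sided test at n = 15 has about 85% power or more. This stands. It also shows that a hypothesis about the median says little on how often the device is rated below best.

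Three further objections have weight. This is a titled pilot that disclaims power, so there is no faulty power calculation to correct. The function sentence refers to endpoints in the plural and is not tied explicitly to the Wilcoxon test, so it may mean plain observation of whether the device works. And no passage gives a rule that reads non-significance as success, so misreporting is a risk, not a stated intention.

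None of this supplies a basis for the word sufficient. A pilot needs no power, but a sentence claiming that its size supports a comparative conclusion needs some reason, and none is given. The only argument offered on the control side is that its median is assumed to be 4.0. That compares the device with an assumption, not with the randomised controls.

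**Conclusion.** The sufficiency claim for function against control is unsupported and should be withdrawn. The missing between-arm comparison is at least as much the cause as the sample size: no number of patients would make a one-sample test against 4.0 a comparison with control, or make its non-rejection proof of adequate function.

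The size adds to the problem. On the exact two-sided 5% test, a shortfall in 30% of uses is detected 28% of the time at 15 per group. Other two-sided versions reach 49% or 70% with tied scores. Only the most lenient version examined (one-sided, uncorrected, tied) exceeds 80%. These figures rest on 4.0 being the top score, independent ratings and an assumed share below best.

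The point does not extend to the bruising half of the sentence, and it is not a charge of wrong arithmetic.

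**What to change.** Replace the function part of the sample-size sentence in the SAP with text such as:

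> The sample size was chosen for practicality and is not sufficient to conclude that the TPAD functions as intended relative to control. Questionnaire results will be given by arm, with the between-arm difference and its 95% confidence interval. At 15 per group the half-width for a difference in the proportion rated below best is roughly 21 to 36 percentage points, depending on the true proportions. A non-significant test against 4.0 will not be read as evidence of adequate function.

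The 21 to 36 range corresponds to proportions from 10% to 50% in both arms. If the Protocol's 10 per arm is the true target, the range becomes about 26 to 44. Reconcile Protocol sections 1.a and 2.g (10 per arm) with Protocol section 8.a (30 planned) and the SAP (15 per group). If the test against 4.0 is kept, state its level, sidedness, p-value method and handling of zeros and ties.

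The cost is wording, plus one added descriptive comparison. No extra patients are needed and study procedures do not change. The downside for the sponsor is a less favourable statement of what the trial can show.
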